3 OBJECTIVES AND ENDPOINTS

Provide a description of the study objectives and endpoints, as well as a justification for selecting the particular endpoints, in the table format included below. This will provide clear articulation of how the selected primary and secondary endpoint(s) are linked to achieving the primary and secondary objectives and an explanation of why endpoint(s) were chosen. Data points collected in the study should support an objective or have a regulatory purpose. Therefore, careful consideration should be given prospectively to the amount of data needed to support the study's objectives.

An **objective** is the purpose for performing the study in terms of the scientific question to be answered. Express each objective as a statement of purpose (e.g., to assess, to determine, to compare, to evaluate) and include the general purpose (e.g., feasibility, acceptability, engagement of the intervention target, identifying mechanisms of action, mediation, moderation, efficacy, effectiveness, dissemination, implementation).

A study **endpoint** is a specific measurement or observation to assess the effect of the study intervention. Study endpoints should be prioritized and should correspond to the study objectives and hypotheses being tested. Give succinct and precise definitions of the study endpoints used to address the study's primary objective and secondary objectives (e.g., specific diagnostic tests that define safety or efficacy, clinical assessments of disease status, assessments of psychosocial characteristics, patient reported outcomes, behaviors or health outcomes). A full description of study endpoints, including administration, scoring, psychometrics, adjudication of endpoints, etc., belongs in **Section 8, Study Assessments and Procedures**.

A putative mechanism of action is the theorized explanation for how the intervention functions.

Consider whether primary and secondary endpoints should be adjusted for multiple comparisons, family-wise error rates, alpha inflation, etc. Details of any such adjustments should be included in **Section 9.4.2, Analysis of the Primary Endpoint(s)** and **Section 9.4.3, Analysis of the Secondary Endpoint(s)**.

OBJECTIVES	ENDPOINTS	JUSTIFICATION FOR ENDPOINTS
Primary		
To evaluate whether the intervention increases CRC screening in noncompliant African American men.	
Medical Records Review verification of colorectal cancer screening since study entrySelf-report of CRC screening since study entry	Tests causal mechanism
Secondary		
To evaluate whether the intervention improves health beliefs and knowledge in noncompliant African American men.	
Perceived severity of CRCPerceived susceptibility to CRCPerceived barriers to colonoscopy and stool testsPerceived benefits of colonoscopy and stool testsTrust in the medical system	Tests causal mechanism or potential moderating effects

OBJECTIVES	ENDPOINTS	JUSTIFICATION FOR ENDPOINTS
	
• CRC knowledge	

4 STUDY DESIGN

No text is to be entered in this section; rather it should be included under the relevant subheadings below.

4.1 OVERALL DESIGN

This is a Phase II single-site randomized, 2-arm between-subjects study examining differences in CRC screening and related beliefs between participants randomized to the experimental intervention and those randomized to the attention control condition (text messages providing CRC information and links to CDC-developed videos). Outcomes were assessed at baseline and again at 6-months post-baseline. We hypothesized that experimental participants would be more likely to get screened for CRC and report more positive beliefs about screening than control participants. Participants were assigned to conditions by an algorithm programmed into the study computer using a permuted blocks randomization scheme. Blocks of size 4 and 6 were used. Assignments within blocks was be random but balanced among the two conditions and the order of the blocks (4 vs 6) also was random. This procedure will ensure that the number of participants randomized to each condition was equal, that any imbalance among the conditions at any point during the recruitment and randomization was modest, and that it would be very difficult to guess the assignment of the next participant. Randomization was administered via computer-based admin system and triggered by the study coordinator.

The intervention – m-CRCSi – combines text messages with brief educational and motivational videos to provide CRC education, reduce screening barriers, and promote timely screening.

4.2 SCIENTIFIC RATIONALE FOR STUDY DESIGN

Participants in the control condition received a text explaining that over the next several weeks they would be receiving information about CRC developed by the CDC. Over the next 8 weeks, users receive 16 text messages with either information about CRC or links to CDC-developed videos about CRC. These texts and videos include information about CRC, CRC screening tests, barriers and benefits to CRC screening, and other health-related beliefs about CRC. This control condition was chosen to provide a close match to the content, format, and delivery schedule of the experimental intervention. This study design was chosen to allow for a comparison between the m-CRCSi intervention and widely available video-based content developed by the leading public health agency protecting the health of Americans.

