1 PROTOCOL SUMMARY

1.1 SYNOPSIS

Title:	Reducing Colorectal Cancer Health Disparities: An mHealth Intervention to Improve Screening among African American Men
Grant Number:	R44CA246899
Study Description:	Two-arm, parallel-group randomized controlled trial comparing a tailored, SMS-delivered mobile education program with attention-control (CDC video links) to improve completion of any guideline-concordant colorectal cancer (CRC) screening by ~6 months among Black/African American men who are non-adherent to CRC screening.
Objectives*:	Objectives: Primary—evaluate effect on completion of any guideline-concordant CRC screening since enrollment. Secondary—evaluate effects on CRC beliefs (severity, susceptibility, benefits/barriers), knowledge, self-efficacy, and medical trust.
Endpoints*:	Endpoints: Primary—binary indicator of any CRC screening since enrollment assessed at follow-up. Secondary—validated scale scores at baseline and follow-up.
Study Population:	Black/African American men who are aged 45–75, non-adherent to CRC screening, and smartphone owners in Washington, DC
Phase* or Stage:	Phase II clinical trial
Description of Sites/Facilities Enrolling Participants:	Single U.S. community health center in Washington, DC
Description of Study Intervention/Experimental Manipulation:	The study intervention includes a structured series of text messages that deliver links to brief, mobile-friendly videos on colorectal cancer risk, guideline-recommended screening options (FIT/FOBT, FIT-DNA, colonoscopy, CT colonography, and flexible sigmoidoscopy), and strategies to overcome common barriers. Messages are automated and paced over approximately 6–9 weeks, resulting in an estimated total exposure of about two hours of content. Comparator: CDC-developed CRC education links delivered by SMS and paced over 6 weeks. Estimated video length is 30–40 minutes total.
Study Duration*:	18 months
Participant Duration:	6 months

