2.1 STUDY RATIONALE

Colorectal cancer (CRC), the second overall leading cause of cancer death, is particularly burdensome for African American men, who have high incidence of the disease with lower survival rates at all CRC stages.

Screening (e.g., colonoscopy, stool-based tests) can prevent most cases of invasive CRC. However, uptake is inadequate, especially among low SES African American men. Most efforts to increase CRC screening in this group utilize in-person or telephone-based education and navigation. While effective, these approaches are resource intensive, limiting their adoption by organizations that serve low SES Black men, such as Federally Qualified Health Centers (FQHCs).

To address the need for an effective, affordable, and scalable strategy to increase CRC screening among African American men, this project developed a mobile colorectal cancer screening intervention (m-CRCSi) for this group. m-CRCSi is based on the health belief model (HBM) and delivered via mobile phone. It includes text messages designed to improve CRC knowledge and health beliefs. Some text messages include links to videos, including educational instruction and unscripted peer narratives. Program content is designed to reduce health literacy barriers and promote CRC screening adherence.

A prototype m-CRCSi was developed in Phase I. This development was informed by formative research with community-based care providers and target end-users. The results of Phase I far exceeded the proposed benchmarks and strongly support the usability, acceptability, and potential effectiveness of the intervention.

During Phase II we completed development of the m-CRCSi. Then, in collaboration with Family and Medical Counseling Service (our partner FQHC), we examined the effectiveness of the m-CRCSi to increase CRC screening in African American men. Participants were randomly assigned to either the intervention condition or to a matched control condition. Secondary measures assessed health beliefs, trust in the medical system, and knowledge.

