6.1.2 ADMINISTRATION AND/OR DOSING

Participants in the intervention arm receive a fully automated, mobile program that blends short, pre-recorded video chapters with behaviorally informed SMS prompts. Delivery is remote and device-based (links arrive by text; videos open on the participant's phone), so all exposure occurs in participants' everyday settings rather than in clinic (video host "William," a health educator, introduces and guides the experience). The curriculum phase consists of a sequenced video pathway with five content areas: (0) Orientation/how-to; (1) CRC basics and screening rationale; (2) a tailored "Your Screening Plan"; (3) colonoscopy skills/support; and (4) stool-test skills/support, followed by (5) "Roadblocks" with practical workarounds. This structure (multiple brief videos per chapter) is scripted and enumerated in the master outline. A complete ("full-dose") curriculum exposure is defined as viewing the core chapter set (0–5) with the tailored branch in Chapter 2 (average- vs high-risk; screened vs unscreened) and the colonoscopy and/or stool-test micro-modules appropriate to that branch. Immediately after education, participants enter a Post-Education Screening Assistance (PESA) phase driven by SMS logic. This phase checks status, offers tips/resources, and schedules periodic reminders keyed to whether a colonoscopy or stool test is planned, scheduled, completed, or not planned. Example schedules include check-ins and supports at 2, 3, 5, 6, 8, 10, 12, 14 days and beyond, with the system extending supportive messaging out to roughly 16 weeks (e.g., 88, 94, 100, 108, and 116 days since the initial PESA trigger).

Curriculum frequency/intensity. Videos are brief (micro-learning format) and delivered via SMS links in sequence; the program advances if a user stalls, with nudges to keep momentum. The curriculum comprises multiple short videos across Chapters 0–5; for dose accounting, we treat each chapter as a "session," yielding ~5 sessions for a full curriculum dose (with additional sub-sessions in the tailored Chapter 2 branch and the chosen test-skills modules).

PESA frequency/intensity. After education, SMS prompts occur on a fixed timer and/or when users report milestones (e.g., "scheduled in 2–4 weeks," "don't know date yet," "planning to schedule"). Messages cluster early (2–10 days), then taper while extending for up to ~116 days if screening has not yet occurred.

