6.2.1 INTERVENTIONIST TRAINING AND TRACKING

Timed text messages – called nudges – are sent to experimental participants at pre-specified intervals if they have not engaged with or completed a video chapter. After 7 days, an autodrop of the next chapter is triggered even if participants have not completed the previous chapter. Although no one “administers” the intervention content, study staff may assist with enrollment logistics and basic tech support. Staff will not advise on screening choices or alter message timing/content. If a participant becomes “stalled” (i.e., they have not engaged with intervention content in over 7 days and have not completed the intervention), an email message is sent to the study coordinator. The study coordinator then contacts the participant to inquire about any issues or questions and reinforce the importance of engaging with the intervention.

To ensure consistent delivery across arms, we will perform routine quality control (QC) checks using the SMS platform’s audit logs and dashboards. QC procedures include: (a) automated monitoring of send failures (hard/soft bounces) with daily review and same-day re-send or number verification; (b) timing-drift checks comparing scheduled vs. actual send times (tolerance ± 5 minutes for fixed-time sends; ± 24 hours for week-based sequences) with corrective action logged; (c) weekly link-uptime validation (HTTP status and redirect integrity) for all URLs in both arms, with broken links replaced from a preapproved list; and (d) parity audits to confirm equivalent contact frequency and timing windows across study arms. All QC activities are documented in an audit trail (issue, detection date, corrective action, verification). Responsibility: Study Technologist (daily automated checks) and Project Manager (weekly parity audit); oversight by the PI.

Control fidelity is tracked via delivery logs, weekly link checks, and audit reports confirming scheduled sends and link availability.

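### The control is described as a close match to the intervention, but on the protocol's own figures amount and duration of contact differ, so an effect can be credited only to the whole package

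*Combined protocol and SAP*

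**What the plan says.** **The matching claim.** Section 4.2 gives as the reason for the comparator: "This control condition was chosen to provide a close match to the content, format, and delivery schedule of the experimental intervention". Section 2.1 says that participants were assigned to the intervention or "to a matched control condition". Sections 1.1, 4.1 and 6.1.1 use the term attention control.

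**The amounts.** For the experimental arm, the synopsis (Section 1.1) states an "estimated total exposure of about two hours of content", paced over roughly 6–9 weeks. For the control it states: "Estimated video length is 30–40 minutes total".

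**The contact schedules.** Section 6.1.2 adds a post-education assistance phase to the experimental arm. It consists of status checks, resources and reminders that cluster early and then taper, "extending for up to ~116 days if screening has not yet occurred". Section 6.2.1 adds timed nudges, automatic release of the next chapter, and a contact from the study coordinator when a participant stalls. The control is described as running for 6 weeks in Section 1.1 and for 8 weeks in Sections 4.2, 6.1.1 and 6.1.2. The schedule of activities (Section 1.3) marks the control intervention in both Day 2–60 and Day 61–180, and the experimental intervention in Day 2–60 only.

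**The audit.** Item (d) of the quality checks in Section 6.2.1 requires "parity audits to confirm equivalent contact frequency and timing windows across study arms", with the project manager responsible each week.

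**The concern.** A matched attention control serves to hold contact time and attention constant, so that a difference between arms points to what the intervention says rather than how much of it there is. Here several things differ at once: tailoring, volume of content, length of contact, reminders and coordinator contact. The reminders matter most, because they bear directly on the primary endpoint: they follow whether a test is planned, scheduled or done.

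If the matching language is carried into the report, readers will take a positive result as evidence for the tailored content at equal attention. The table in Section 3 encourages this by justifying the primary endpoint as a test of causal mechanism. The data could not settle the question afterwards, because Section 6.4 says that control click-throughs and time on page are not collected.

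There is also a practical conflict. Audit item (d) asks staff to confirm an equivalence that the described schedules do not have once the curriculum phase is over.

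**Working it through.** The plan states no ratio and no total contact time, so there is no planned figure to reproduce. The arithmetic below uses its stated inputs.

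**1. Content ratio.** Inputs from Section 1.1: about two hours = 120 minutes; control 30–40 minutes.
- 120 / 40 = 3.0
- 120 / 30 = 4.0

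The first input is total exposure and the second is video length, so the ratio is approximate. Two sensitivity checks, each resting on an assumption that is not in the documents:
- If about two hours means 100–140 minutes: 100 / 40 = 2.5 to 140 / 30 = 4.7.
- If each of the 16 control texts adds 0.25–1 minute of reading (4–16 minutes in all) and nothing is added to the experimental arm: 120 / (40 + 16) = 2.1 to 120 / (30 + 4) = 3.5.

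The control has less content in every case.

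**2. Length of message contact for a man not yet screened.** Inputs: curriculum of 6–9 weeks (Section 1.1); up to 116 days after the assistance phase is triggered, with that phase starting immediately after education (Section 6.1.2); control of 6 weeks (Section 1.1) or 8 weeks (Sections 4.2, 6.1.1, 6.1.2).
- Experimental: 6 × 7 + 116 = 158 days, to 9 × 7 + 116 = 179 days.
- Control: 6 × 7 = 42 days, or 8 × 7 = 56 days.
- Ratio: 158 / 56 = 2.8 to 179 / 42 = 4.3.
- Share of a 180-day window in which only the experimental arm is described as being messaged: (158 − 56) / 180 = 57% to (179 − 42) / 180 = 76%.

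These are maxima. Section 6.4 closes the program when screening is reported. They also follow the text of Sections 1.1 and 6.1.2, with which Section 1.3 disagrees.

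**3. Elements present in one arm only.** Section 6.1.2 names 13 example contact days in the assistance phase: eight from day 2 to day 14, and five from day 88 to day 116. No corresponding phase is described for the control. Section 6.2.1 describes nudges for experimental participants. It ties coordinator contact to stalled progress through intervention content. Since control engagement is not recorded (Section 6.4), a stalled control participant could not be detected.

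**4. Contact after Day 60.** Section 1.3 places the control, and not the experimental arm, in Day 61–180. Section 6.1.2 describes the reverse: a control of 8 weeks (56 days), and an experimental arm with messages for up to about 116 days after education. The documents do not show which is right.

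**5. What audit item (d) can show.** The control receives 16 texts over 8 weeks, or 2 per week (Sections 4.2 and 6.1.1), or 1–2 per week, which is 8–16 texts (Section 6.1.2). The number of experimental texts during the curriculum is not given, so equality or inequality of frequency in weeks 1–8 cannot be established. A mismatch can be shown only after the curriculum phase.

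**The case against.** The strongest reply is that the protocol never claims to isolate tailoring. The sentence after the quoted one in Section 4.2 gives the purpose as comparing m-CRCSi with widely available CDC video content, and the primary hypothesis in Section 9.1 is about the intervention as a whole. This stands. A reader might infer that the primary comparison is invalid, or that the trial claims an effect of tailored content alone; the documents support neither.

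Second, Section 4.2 claims a match on content, format and delivery schedule, not on minutes. The topics overlap, both arms use texts with video links, and 8 weeks lies within 6–9 weeks. This stands in part: it would be wrong to call the statement untrue in every respect. But the text does not limit the schedule claim to the curriculum phase, and matched and attention control are naturally read as covering amount of contact.

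Third, a reader might infer that the control receives nothing after week 8. No section says so. The inference rests on silence, and Section 1.3 points the other way. That table carries leftover template wording and conflicts with Section 6.1.2, so it does not prove that control contact continued; it shows only that the sections disagree.

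Fourth, a reader might infer that the parity audit must fail throughout. That is not shown for weeks 1–8, for the reason in step 5 of the working, and the audit feeds no endpoint or analysis.

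**Conclusion.** The point holds as a mismatch between the description of the comparator and the described schedules. Content differs roughly 3–4 fold (2.1 to 4.7 under the sensitivity assumptions). On the text of Sections 1.1 and 6.1.2, message contact for a man not yet screened lasts up to about 2.8 to 4.3 times as long in the experimental arm. Nudges, stalled-participant contact and the reminder phase are described for that arm only.

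The randomized test of the whole program against CDC materials is unaffected, and no estimate, test or sample size changes. What changes is the conclusion: an effect could not be separated into tailoring, volume, contact and reminders. Audit item (d) cannot be met as written beyond the curriculum phase if the Section 6.1.2 schedules apply. The duration figures depend on how the conflict with Section 1.3 is resolved; the content ratio does not. This should be corrected, but it does not threaten the trial.

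**What to change.** - Remove or qualify the matching and attention-control wording in Sections 1.1, 2.1, 4.1, 4.2 and 6.1.1. It is accurate to say that topics and format are similar.
- State that the conclusion is limited to the whole package (content, amount and reminder phase) against CDC materials, and carry this into the report and the posted results.
- Reconcile Sections 1.1, 1.3, 4.2, 6.1.1 and 6.1.2 on when each arm is contacted, including the 6-week and 8-week control durations and the Day 61–180 entries.
- Replace audit item (d) in Section 6.2.1 with a check of each arm against its own schedule, or limit it to the period when both arms are scheduled for contact.
- Report messages delivered by arm. Section 6.4 already has send logs for the control and plans a delivery summary, so no new data are needed.

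No change of dose or schedule is proposed. The cost is protocol wording, one extra table and a narrower claim. Section 1.2 already gives arm sizes of 63 and 65, so enrollment may be over; the wording, the reconciliation and the delivery table can still be done at reporting.

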4.3 JUSTIFICATION FOR INTERVENTION

m-CRCSi is an effective, affordable, and scalable intervention to increase CRC screening among African American men. The intervention is based on the Health Belief Model (HBM). The HBM posits that a person is more likely to perform a health behavior when he: understands the seriousness of an illness (perceived severity) and feels there is a realistic chance he will develop it (perceived susceptibility), expects that the health behavior will reduce risks from the illness (perceived benefits) with relatively few costs (perceived barriers), is aware of the health behavior (cues to action), and believes he can perform it (self-efficacy). The intervention integrates text messages and videos because the majority of African American men own and use smartphones. Delivered across 5 “chapters,” the videos are designed to address potential health literacy concerns by providing brief and clear information about CRC and screening options. It is expected that men will engage with all intervention content.

